## Summary of Clinical Trial Design

	Baseline	Week 4	Week 8	Week 12	Week 16	Week 20
Crisaborole 2% ointment twice daily	x	x	x	x		
Clinic visit	x	x	x	x		x
LoSCAT scoring	x	x	x	x		x
DIET scoring	x	x	x	x		x
Skin punch biopsy	x			x		
Urine HCG	x	x	x	x		
Skindex 29	x	x	x	x		x
Skin imaging (ultrasound)	x	x	x	x		x
Photography	x			x		x

**Primary outcome measure** is the change in dermal thickness on skin biopsy at 12 weeks.

**Secondary outcome measures** are the following:

- Change in DIET score of sentinel plaque at 4, 8 and 12 weeks.

- Change in LoSCAT score at 4, 8 and 12 weeks.
- Skindex-29 at 4, 8 and 12 weeks.
- Change in dermal thickness of sentinel plaque by ultrasonography at 4, 8 and 12 weeks

## 5. Selection of Subjects:

### Inclusion criteria

Subjects eligible for inclusion in this study must fulfill **all** of the following criteria:

1.  $\geq 18$  years of age
2. Clinical diagnosis of morphea.
3.  $<20\%$  Total body surface area involvement.
4. Does not require systemic immunosuppressive therapy for morphea.
5. No changes (additions, subtractions, or dose modifications) in immunosuppressive systemic therapy 2 months prior to starting the study (hydroxychloroquine, methotrexate, mycophenolate mofetil, azathioprine, cyclosporine, cyclophosphamide, prednisone  $\geq 10$  mg PO daily).
6. No immunomodulating topical therapy (topical steroids or topical calcineurin inhibitor), and no topical vitamin D analogue, 2 weeks prior to starting study.
7. No allergy to crisaborole or vehicle.
8. No known renal disease
9. Able to give informed consent.

### Exclusion Criteria

Subjects fulfilling **any** of the following criteria are not eligible for inclusion in this study.

1. Clinical diagnosis of depression or history of suicidal ideation.
2. Pregnant or breastfeeding women, with pregnant women being defined as the state of a female after conception until the termination of gestation, confirmed by a positive urine human chorionic gonadotropin (hCG) laboratory test. Women with a positive urine hCG at any time during the study will be withdrawn from the study.

## 6. Subject Recruitment & Compensation:

Patients will be recruited from the Duke Dermatology Outpatient Clinic, including patients referred from Rheumatology for evaluation of morphea. We may also contact dermatologists in the community (within North Carolina), UNC Dermatology, Wake Forest Dermatology and the Durham VA Medical Center, via email and letter, to make them aware of our study so they can refer patients. Prior to any recruiting outside the Duke Derm Autoimmune clinics, we will seek approval for any flyers that are used in recruitment and provide a phone script for those who respond to flyers.

Patients will be given compensation to cover travel expenses as part of their participation in the study, amounting to \$50 per visit, or a maximum of \$250. A gift card worth \$50 will be given at baseline, week 4, week 8 and week 12. A final \$50 gift card will be given at the optional week 20 visit, should they choose to participate in it.

**7. Consent Process** – see Section 14 of the e-IRB submission form.

**8. Subject's Capacity to Give Legally Effective Consent:**

Subjects must be able to provide consent. Legal representatives will not be used.

**9. Study Interventions:**

Subjects will be asked to apply crisaborole 2% ointment, twice daily, on affected plaques for 12 weeks.

**10. Risk/Benefit Assessment and Safety Considerations:**

If a subject agrees to take part in this study, there may not be a direct medical benefit to them. The subject's morphea may improve from using the investigational drug in this study. It is also possible that a subject's condition will not improve on the investigational drug.

The pharmacokinetics of crisaborole as a topical medication have previously been studied. Crisaborole is metabolized to inactive metabolites upon absorption, making it both a safe option for therapy even in relatively extensive disease. There was minimal systemic effect of crisaborole ointment when applied twice daily for 28 days, over up to 35% body surface area, in children 2-17 years of age. Long term studies in adults and children with mild to moderate atopic dermatitis for as long as 48 weeks have also shown a low frequency of side effects. The most frequently reported treatment-related AEs (overall, 10.2%) were worsening of pre-existing atopic dermatitis (3.1%), application-site pain (2.3%), and application-site infection (1.2%). The FDA monograph of crisaborole does not state any requirement for monitoring.

The risks for obtaining skin biopsy samples include a mild amount of pain, bruising, bleeding, or infection at the site of the puncture. Subjects will be instructed in proper wound care to minimize these risks. Subjects may experience scarring at the site of biopsy.

**11. Costs to the Subject:**

There will be no additional costs to the subjects as a result of being in this study. However, routine medical care for their disease will be charged to them or their insurance company.

**12. Data Analysis & Statistical Considerations:**

We will aim to recruit 20 patients in the study. We anticipate to see a 30% decrease in dermal thickness at 12 weeks compared to baseline, using histologic evaluation of skin punch biopsy specimens. Using measurements of dermal thickness that we obtained from our archived morphea skin biopsies, we estimated that we need 11 patients to detect 30% change in dermal thickness with a power of 0.80 and an alpha of 0.05. The goal to recruit 20 patients allows for possible drop-outs, while still allowing us to perform statistically significant analysis.

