**Skin punch biopsy of sentinel plaque:**

A sentinel plaque will be selected at baseline. A 4 mm skin punch biopsy will be performed at baseline and at 12 weeks, on the same affected plaque.

If a biopsy has been previously taken of the affected plaque and is available for review, this will be used as the baseline biopsy. Patients who drop out of the study because of progression of their disease or adverse effects will undergo a skin punch biopsy at the time of drop out.

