**Numeric Results for Wilcoxon Test (Normal Distribution)**  
Null Hypothesis: Mean of Paired Differences = 0, Alternative Hypothesis: Mean of Paired Differences  $\neq$  0  
Unknown standard deviation.

Power	N	Alpha	Beta	Mean of Paired Differences	S Size	Effect
0.81293	4	0.05000	0.18707	1.0	0.3 3.333	
0.89861	5	0.05000	0.10139	1.0	0.4 2.500	
0.90888	6	0.05000	0.09112	1.0	0.5 2.000	
0.89877	7	0.05000	0.10123	1.0	0.6 1.667	
0.87994	8	0.05000	0.12006	1.0	0.7 1.429	
0.85644	9	0.05000	0.14356	1.0	0.8 1.250	
0.83039	10	0.05000	0.16961	1.0	0.9 1.111	
0.80310	11	0.05000	0.19690	1.0	1.0 1.000	
0.84753	12	0.05000	0.15247	1.0	1.0 1.000	
0.80310	11	0.05000	0.19690	0.5	0.5 1.000	
0.82792	9	0.05000	0.17208	0.6	0.5 1.200	
0.86733	8	0.05000	0.13267	0.7	0.5 1.400	
0.87508	7	0.05000	0.12492	0.8	0.5 1.600	
0.84741	6	0.05000	0.15259	0.9	0.5 1.800	
0.90888	6	0.05000	0.09112	1.0	0.5 2.000	

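### Does the sample size of 11 need revisiting because the plan does not show how a 30% change in dermal thickness becomes an effect size of 1.0?

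*Combined protocol and SAP*

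**What the plan says.** The primary outcome, under Summary of Clinical Trial Design, "is the change in dermal thickness on skin biopsy at 12 weeks". Section 12 sets the expected effect: "We anticipate to see a 30% decrease in dermal thickness at 12 weeks compared to baseline". It names the source of the planning data, "Using measurements of dermal thickness that we obtained from our archived morphea skin biopsies", and concludes "we estimated that we need 11 patients to detect 30% change in dermal thickness with a power of 0.80 and an alpha of 0.05". It then justifies the larger target: "The goal to recruit 20 patients allows for possible drop-outs, while still allowing us to perform statistically significant analysis".

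The table that follows is for a two-sided paired Wilcoxon test with normally distributed differences. Its mean differences run from 0.5 to 1.0 and its SDs (column S) from 0.3 to 1.0, without units. N=11 appears twice, at 1.0/1.0 and at 0.5/0.5. Both rows have effect size 1.000 and power 0.80310.

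**The concern.** The text speaks of a percentage change, the table of a standardised one, and nothing joins them. The plan does not give the mean thickness in the archived biopsies, their SD, their number, the units, or whether they were before-and-after pairs. A reader cannot confirm that 30% amounts to at least one SD of the paired differences.

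This looks serious because both sample-size statements rest on that step. If the SD of change were well above 30% of baseline, 11 patients would be too few, and the margin between 11 and 20 would cover fewer losses than Section 12 implies. If the archived specimens were single biopsies, they would describe variation between patients, and the SD of within-patient change would need a further assumption. The table's N=4 and N=5 rows also print powers (0.81293 and 0.89861) that an exact test cannot have, which could cast doubt on the rest.

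**Working it through.** **Inputs.** From Section 12: two-sided alpha 0.05, N=11, target 20, mean change 30% of baseline, and the table's mean differences and SDs. The SD of paired change as a percentage of baseline is not in the documents, so a range of 25% to 50% is assumed below.

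**1. Reproducing the table.** Take effect size d = mean difference / S and n = 3N/π rounded down. Power is that of a two-sided paired t-test with n − 1 degrees of freedom and noncentrality d√n.

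- N=11, d=1: 33/π = 10.50, so n = 10 and the noncentrality is √10 = 3.162. Power is 0.80310, as printed.
- N=12, d=1: 36/π = 11.46, so n = 11. Power is 0.84753, as printed.
- The other 13 rows also agree to five decimals.

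An exact signed-rank test (simulated, normal differences, d=1) gives power 0.784 at N=10, 0.809 at N=11 and 0.985 at N=20. The exact method also gives 11 as the smallest N reaching 80%.

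**2. What N=11 implies for a 30% change.** With d = 30 / SD (SD in % of baseline), 80% power needs:

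- N=11: d = 0.996 by the table's method, so SD ≤ 30/0.996 = 30.1%. The exact test needs d = 0.989, so SD ≤ 30/0.989 = 30.3%.
- N=20: d = 0.680 by the table's method, so SD ≤ 30/0.680 = 44.1%. The exact test also gives about 44%.

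**3. Power over the assumed range** (exact test, 30% mean change):

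| SD of change, % of baseline | d | Power, N=11 | Power, N=20 |
|---|---|---|---|
| 25 | 1.20 | 0.93 | 0.999 |
| 30 | 1.00 | 0.81 | 0.985 |
| 35 | 0.86 | 0.68 | 0.94 |
| 40 | 0.75 | 0.56 | 0.87 |
| 45 | 0.67 | 0.47 | 0.79 |
| 50 | 0.60 | 0.39 | 0.70 |

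At the implied SD of 30%, the target leaves 20 − 11 = 9 pairs to spare (9/20 = 45%). At larger SDs the margin shrinks, and its exact size depends on the method. At 40%, the exact test needs 18 pairs (17 give 0.796) and the table's method needs 17, so the margin is 2 or 3.

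**4. If the archived biopsies were single specimens.** With equal variances before and after, SD of change = CV × √(2(1 − r)), where CV is the between-patient SD as a share of baseline and r the within-patient correlation. For an assumed CV of 30%, this gives 23.2% at r = 0.7, 30.0% at r = 0.5, 35.5% at r = 0.3 and 42.4% at r = 0. All four lie below the 44% that 20 complete pairs can carry.

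**5. The smallest rows.** The minimum two-sided signed-rank p-value is 2/2⁴ = 0.125 at N=4 and 2/2⁵ = 0.0625 at N=5. Exact power at the 0.05 level is therefore zero in both rows. The table's t-based approximation breaks down there. It does not at N=11, where it gives 0.803 against 0.81 exact.

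**The case for a change.** The strongest opposing case is that a protocol making a specific power claim should let a reader check it, and this one does not. The missing SD governs the primary endpoint. At 25% of baseline, 20 patients are ample; at 45%, even 20 complete pairs fall just short of 80%. The investigators say they hold the measurements, so stating them would cost a paragraph.

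Much of that stands. The step from 30% to effect size 1.0 is missing, and the stated power is conditional on it. But the argument shows an unverified input, not a wrong one, since the SD may be favourable or unfavourable. Not knowing which N=11 row was meant is harmless, because both have the same effect size, N and power. Lost patients are also not the same as lost pairs: Section 4 calls for a biopsy when a patient leaves because of progression or adverse effects, although it does not say whether that specimen enters the primary comparison. Counts of tolerable losses are therefore approximate.

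Section 4 also says "If a biopsy has been previously taken of the affected plaque and is available for review, this will be used as the baseline biopsy", with no limit on that specimen's age. That is a question about what the endpoint measures. No figure in the documents ties it to the planning SD, so it does not bear on the 11.

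**Conclusion.** No change to the plan follows. The figure of 11 is correctly computed for an effect size of 1.0, and what is missing is a record of how the archived data led there. Supplying it would not alter the target of 20, the visits, the biopsies or the test. A signed-rank test on the observed differences does not use the planning SD, so the trial's result would be the same.

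The target also absorbs a good deal of error in the unstated SD. Power at 20 pairs is about 98% if the SD of change is 30% of baseline, and stays above 80% up to about 44%. That is a reasonable position for a single-arm pilot. These figures assume normally distributed differences, a true mean change of 30% and all 20 patients supplying pairs; with losses, the tolerable SD falls towards 30% at 11 pairs. The N=4 and N=5 rows are a flaw in an illustrative table, and no decision rests on them.

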**Numeric Results for Wilcoxon Test (Normal Distribution)**  
Null Hypothesis: Mean of Paired Differences = 0, Alternative Hypothesis: Mean of Paired Differences  $\neq$  0  
Unknown standard deviation.

Power	N	Alpha	Beta	Mean of Paired Differences	S Size	Effect
0.81293	4	0.05000	0.18707	1.0	0.3 3.333	
0.89861	5	0.05000	0.10139	1.0	0.4 2.500	
0.90888	6	0.05000	0.09112	1.0	0.5 2.000	
0.89877	7	0.05000	0.10123	1.0	0.6 1.667	
0.87994	8	0.05000	0.12006	1.0	0.7 1.429	
0.85644	9	0.05000	0.14356	1.0	0.8 1.250	
0.83039	10	0.05000	0.16961	1.0	0.9 1.111	
0.80310	11	0.05000	0.19690	1.0	1.0 1.000	
0.84753	12	0.05000	0.15247	1.0	1.0 1.000	
0.80310	11	0.05000	0.19690	0.5	0.5 1.000	
0.82792	9	0.05000	0.17208	0.6	0.5 1.200	
0.86733	8	0.05000	0.13267	0.7	0.5 1.400	
0.87508	7	0.05000	0.12492	0.8	0.5 1.600	
0.84741	6	0.05000	0.15259	0.9	0.5 1.800	
0.90888	6	0.05000	0.09112	1.0	0.5 2.000	

#### References

Women and minority volunteers will be encouraged to enroll, but no formal subgroup accrual goals are planned.

The descriptions and grading scales found in the revised NCI Common Terminology Criteria for Adverse Events (CTCAE) version 4.0 will be utilized for AE reporting.

Months 1-6	Months 7-12	Months 13-18	Months 19-24
Subject recruitment (1-2 patients per month), clinical and objective assessment, collection of biopsies			Genomic profiling, data interpretation and analysis, and paper writing.

### 13. Data & Safety Monitoring:

Subjects will be assigned unique study numbers. The data related to this study will be kept in locked files and an electronic password protected database maintained by the Department of Dermatology research offices. Only unique study numbers but not DUMC history numbers will be supplied as subject IDs for data maintenance and statistical analysis purposes to comply with HIPAA regulations. This study will have routine auditing consistent with Duke Clinical Research Institute and NIH oversights. Subject confidentiality will be maintained.

All samples will be stored and maintained through the conclusion of the study and then destroyed, unless the subjects agree (and separately consent) to the Samples and Data being included in the Duke Autoimmune Serum Tissue Bank (Pro00006313) and Duke Immune Mediated Skin Disease Database (Pro00006230).

This clinical research study will be monitored both internally by the PI and externally by the Duke University Medical Center in accord with their NIH- approved “Institutional Protocol Monitoring Procedures and Guidelines for NIH-Sponsored Research Involving Human Subjects.”

**14. Privacy, Data Storage & Confidentiality** – see Section 12 of the e-IRB submission form.

